4.1.6 Packaging, labelling, and re-supply

The investigational products will be provided by BI or a designated CRO. They will be packaged and labelled in accordance with the principles of Good Manufacturing Practice (GMP).

For details of packaging and the description of the label, refer to the ISF.

4.1.7 Storage conditions

Drug supplies will be kept in their original packaging and in a secure limited access storage area according to the recommended storage conditions on the medication label. A temperature log must be maintained for documentation.

If the storage conditions are found to be outside the specified range, the local clinical monitor (as provided in the list of contacts) must be contacted immediately.

4.1.8 Drug accountability

The investigator /pharmacist /investigational drug storage manager will receive the investigational drugs delivered by the sponsor when the following requirements are fulfilled:

- Approval of the trial protocol by the ethics committee
- Availability of a signed and dated clinical trial contract between the sponsor and the head of the investigational site,
- Approval/notification of the regulatory authority, e.g. competent authority,
- Availability of the curriculum vitae of the principal Investigator,
- Availability of a signed and dated clinical trial protocol
- Availability of the proof of a medical license for the principal Investigator

The investigator /pharmacist /investigational drug storage manager must maintain records of the product's delivery to the trial site, the inventory at the site, the use by each subject, and the return to the sponsor or warehouse / drug distribution centre or alternative disposal of

Proprietary confidential information © 2017 Boehringer Ingelheim International GmbH or one or more of its affiliated companies

unused products. If applicable, the sponsor or warehouse / drug distribution centre will maintain records of the disposal.

These records will include dates, quantities, batch / serial numbers, expiry ('use- by') dates, and the unique code numbers assigned to the investigational product and trial subjects. The investigator / pharmacist / investigational drug storage manager will maintain records that document adequately that the subjects were provided the doses specified by the CTP and reconcile all investigational products received from the sponsor. At the time of return to the sponsor and/or appointed CRO, the investigator / pharmacist / investigational drug storage manager must verify that all unused or partially used drug supplies have been returned by the clinical trial subject and that no remaining supplies are in the Investigator's possession.

4.2 OTHER TREATMENTS, EMERGENCY PROCEDURES

The study population is restricted to subjects with mild asthma who do not have other significant medical conditions. They have controlled asthma treated adequately with SABA and /or low dose iCS (see Table 4.2.1 for equipotent doses). It is not foreseen that subjects will require other concomitant medications.

Table 4.2: 1 Estimated Equivalent Daily Doses of (low dose) Inhaled Glucocorticosteroids according to GINA 2015 [P15-03654](#).

Drug	Low Dose (µg)
Beclomethasone dipropionate	200-500
Budesonide	200-400
Ciclesonide	80-160
Flunisolide	500-1000
Fluticasone propionate	100-250
Mometasone	200-500
Triamcinolone acetonide	400-1000

4.2.1 Other treatments and emergency procedures

There are no special emergency procedures to be followed.

4.2.1.1 Rescue medication

Administration of rescue medication can occur at any point during the study. Open label salbutamol and /or atrovent MDI will be provided as rescue medication, at screening visit.

If rescue medication is administered during clinic visits (Visits 2– 5), the 24-hour clock time of rescue medication, total number of inhalations of rescue medication used, visit number, date and the name, route and dosage of any additional rescue medication will be recorded on the Rescue Medication eCRF page.

The use of rescue medication during Visits 2 -5 does not necessitate discontinuation of the visit. The subject should remain in the clinic in order to complete the remaining other procedures (see [4.2.2.2](#)).

4.2.2 Restrictions

4.2.2.1 Restrictions regarding concomitant treatment

No concomitant therapy will be allowed except for treatments as specified in [Section 4.2.1](#) above and a low dose of inhaled corticosteroid as defined by GINA guidance [\[P15-03654\]](#), paracetamol or medication for atopic conditions. However, in case of adverse events therapy according to the judgment of the investigator will be permitted. All concomitant therapies and/or rescue therapies will be recorded on the appropriate pages of the case report forms (CRFs). Concomitant medications have to be washed out as defined in [Section 3.3.2](#).

Table 4.2.2.1:1 Overview of Permitted and Restricted Medications

Class	Permission / Restriction and explanation
Inhaled corticosteroids*	Permitted provided equal to or less than 250 µg fluticasone equivalent daily and corticosteroids have been stabilized at least 6 weeks prior to randomisation (Visit 2 i.e Treatment Period 1 Day 1) and will continue to be used during the trial at a stable dose
Paracetamol	Permitted
Intravenous, intramuscular or oral corticosteroids	Not permitted 6 weeks prior screening visit (Visit 1) and during the trial
Oral and patch β-adrenergics	Not permitted 4 weeks prior screening visit (Visit 1) and during the trial
Long acting inhaled β-adrenergics (including fixed dose beta-agonist/ inhaled corticosteroid combinations) ¹	Not permitted 6 weeks prior screening visit (Visit 1) and during the trial.
Short acting inhaled β-adrenergics	Not permitted except for supplied rescue medication. Regarding restrictions for forced spirometry bronchodilators see Section 4.2.2.2 .
Long acting inhaled anticholinergics (e.g. Tiotropium, Aclidinium) (including fixed dose beta-agonist	Not permitted 6 weeks prior screening visit (Visit 1) and during the trial

Proprietary confidential information © 2017 Boehringer Ingelheim International GmbH or one or more of its affiliated companies

/inhaled corticosteroid combinations) ¹	
Short acting inhaled anticholinergics (inhalation aerosol, nasal spray)	Not permitted except for supplied rescue medication. Regarding restrictions for forced spirometry bronchodilators see Section 4.2.2.2
Antihistamines	Not permitted 4 weeks prior screening visit (Visit 1) and during the trial
Cromolyn sodium / nedocromil sodium	Not permitted 4 weeks prior screening visit (Visit 1) and during the trial
Mucolytics	Not permitted 4 weeks prior screening visit (Visit 1) and during the trial
Beta blockers	Permitted provided that beta blockers have been stabilized at least 6 weeks prior to randomisation (Visit 2 i.e: Treatment Period 1 Day 1) and will continue to be used during the trial in a stable manner
Investigational drugs	Not permitted , see exclusion criterion number 17
Antileukotrienes	Not permitted 4 weeks prior screening visit (Visit 1) and during the trial
Theophylline, Aminophylline	Not permitted 4 weeks prior screening visit (Visit 1) and during the trial
A biological based antagonist therapy including Omalizumab, or immune modulators	Not permitted within 6 months of the screening visit (Visit 1)
Non-approved asthma therapies such as methotrexate	Not permitted within 3 months of the screening visit (Visit 1)
Systemically available immunomodulatory treatments for allergic rhinitis or atopic dermatitis.	Not permitted
Medications that may lead to alterations in serum electrolytes (particularly potassium) including but not limited to diuretics**, angiotensin	Not permitted 4 weeks prior screening visit (Visit 1) and during the trial

Proprietary confidential information © 2017 Boehringer Ingelheim International GmbH or one or more of its affiliated companies

convertase/ angiotensin receptor inhibitors***, nonsteroidal anti-inflammatory drugs (NSAIDs)****, cyclosporine or tacrolimus, Pentamidine, Trimethoprim-sulfamethoxazole, Heparin, Ketoconazole and Metyrapone	
---	--

*	Intranasal steroids for atopic condition and topical treatments for eczema are allowed
**	includes spironolactone, amiloride
***	includes Captopril, Zofenopril, enalapril, 52nalyzin, Quinapril, Perindopril, Lisinopril, Benazepril, Imidapril, Trandolapril, Fosinopril, Cilazapril;
****	includes ibuprofen, diclofenac, naproxen, celecoxib, mefenamic acid, etoricoxib, indomethacin, aspirin (doses > 600 mg)

¹ Withdrawal of bronchodilators or reduction in iCS dose is not acceptable unless for medical reasons.

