2.3 BENEFIT - RISK ASSESSMENT

BI 443651 is being developed as a therapy for obstructive airways diseases such as cystic fibrosis and COPD. Participation in this study is without expected (therapeutic) benefit for asthmatic subjects. Their participation in the study is of importance to inform the safety profile of BI 443651 specifically with regard potential adverse effects on lung function prior to progressing to long term clinical studies.

Subjects are exposed to risks related to the study procedures and intake of trial medication as described below.

Procedure-related risks

The use of an indwelling venous catheter for the purpose of blood sampling may be accompanied by mild bruising and also, in rare cases, by transient inflammation of the wall of the vein. In addition, in rare cases a nerve might be injured while inserting the venous catheter, potentially resulting in paresthesia, reduced sensibility, and/or pain for an indefinite period. The same risks apply to venepuncture for blood sampling.

Sampling times and visits may be adapted based on information obtained during trial conduct including addition of samples and visits. The total volume of blood to be withdrawn during the entire study will not exceed 500mL (roughly equivalent to a normal blood donation). No study-related risk to study participants is expected from this blood withdrawal over the course of the study.

Methacholine (MCh) challenge is a routine practice in the diagnosis of asthma in the event of an unclear history or investigations. The main risk is of bronchoconstriction. Pulmonary function will be monitored and adverse findings can be reversed. Adverse effects are expected to be reversible with administration of an inhaled anticholinergic agent (ipratropium bromide) if necessary.

Drug-related risks and safety measures

The nature of the target and the mechanism of action of BI 443651, are well documented. The side effect profile is well understood and the adverse events observed in rats following administration of BI 443651 are consistent with the mechanism.

The animal models are believed to be predictive for the effects in

Proprietary confidential information © 2017 Boehringer Ingelheim International GmbH or one or more of its affiliated companies

humans.

In study 1363.1, 63 healthy male volunteers have been administered single inhaled doses of BI 443651 up to 3600 µg. In this study, BI 443651 was found to be well tolerated (see [Section](#)

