he most sensitive species for these effects was the rat with no relevant effects observed in the dog, even at high doses, on serum or urinary electrolytes. No other systemic safety findings were observed in either the toxicology or safety pharmacology studies.

This translates to a safety margin of approximately 11-fold. The urine cover is regarded as the most relevant exposure for safety based mechanism i.e. serum electrolytes.

BI 443651 does not present a genotoxic hazard. BI 443651 is considered to be low risk for phototoxicity, based on its absorbance pattern and lack of toxicity in 4-week repeat dose studies.

Fertility has not been assessed in nonclinical species, but no adverse effects have been observed on reproductive organs in 4-week toxicity studies in rats and dogs, suggesting that there is a low risk to fertility. At the time this current study is planned to start embryo-fetal development studies of BI 443651 will not yet have been conducted.

Off target inhibition of ACh has been observed with augmented effects in non-clinical ACh/MCh challenge guinea pig models. No adverse effects on pulmonary function were observed in the absence of methacholine or acetylcholine challenge. No adverse respiratory effects were detected in the 4-week toxicology studies or in the safety pharmacology studies at doses of up to 7,750 µg/kg in dog or rat. Exaggerated bronchoconstriction effects may be apparent following methacholine challenge however effects on respiratory function will be monitored and are reversible. Inhaled anticholinergic therapy should reverse these effects if required, as is also used if required for MCh testing.

In summary whilst not all safety effects may be predicted, based on mechanism and systemic toxicological finding the only potential systemic toxicity is changes in serum electrolytes and

Proprietary confidential information © 2017 Boehringer Ingelheim International GmbH or one or more of its affiliated companies

particularly increases in serum potassium. Augmented bronchoconstriction may be induced following administration of methacholine. In both cases these changes are easily monitored and treatable if observed. The following safety measures will be applied in this study in order to minimize the risk for the mild asthmatic subjects:

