- 1 This study (1363.7) will only start once healthy volunteers have been safely administered 100 and 400 µg b.i.d. of BI 443651 for 7days in a separate ongoing study (1363.2) i.e. no stopping criteria have been triggered in 1363.2.
- 2 Only mild, controlled, stable asthma subjects with well-maintained lung function will be included in the study i.e. subjects on prn SABA or low dose inhaled corticosteroid with an $FEV_1 \geq 70\%$ and no recent respiratory tract infection or exacerbation.
- 3 The study will be split into two parts ([see Section 3.1](#)) with an initial pilot (Part 1) to assess for gross adverse effects of BI 443651 on bronchoconstriction after MCh challenge. In Part 1, subjects will receive BI 443651 in a dose ordered fashion with either placebo **or** the lowest dose first followed by the higher doses and placebo (if not taken first). Individual subjects will not be dosed further if individual stopping criteria (including pulmonary function criteria) are triggered. Stopping criteria are described in detail in [Section 3.3.4](#).

The second part of the study (not necessarily dose ordered) will only proceed if no subjects triggered the first three discontinuation criteria following administration of BI 443651 during Part 1.

- 4 The subjects will be closely monitored throughout the treatment period with frequent evaluation of pulmonary function following MCh challenge. Subjects may only be discharged from clinic after medical assessment has been conducted. The subject's FEV_1 must have returned to $\geq 90\%$ of the first set of spirometry measurements performed that day before the subject can be discharged from the clinic. Rescue medication will be provided as required.
- 5 Safety laboratory testing will be performed during the study with a focus on electrolytes ([see Flow Chart](#)). The study will be stopped if, during Part 1 (pilot) at least 2 subjects in the current cohort or treatment period on active drug showed serum potassium levels $\geq 5.5\text{mmol/L}$ in non-haemolysed blood (confirmed by repeat). In Part 2 (main study), the study would be stopped if 4 subjects on active drug (independent of dose level) showed serum potassium levels $\geq 5.5\text{mmol/L}$ in non-haemolysed blood (confirmed by repeat).

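### Protocol Section 4.2.2.1 omits beta blockers from its closed list of allowed therapy, yet Table 4.2.2.1:1 permits stable use without a reason, in an asthma challenge trial with salbutamol as one of two rescue drugs

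*Protocol*

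**What the plan says.** The text of Protocol Section 4.2.2.1 opens with a general bar: "No concomitant therapy will be allowed except for treatments as specified in" Section 4.2.1, which is the rescue medication, together with low-dose inhaled corticosteroid and "paracetamol or medication for atopic conditions". The only relaxation is treatment of adverse events at the investigator's judgement.

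The table that follows, Table 4.2.2.1:1, has a row for beta blockers: "Permitted provided that beta blockers have been stabilized at least 6 weeks prior to randomisation", on condition that use stays stable during the trial. Neither the row nor its footnotes give a reason.

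Section 4.2 describes subjects with mild asthma and no other significant medical condition, and adds: "It is not foreseen that subjects will require other concomitant medications". Section 2.3 describes the population as "subjects on prn SABA or low dose inhaled corticosteroid". Section 4.2.1.1 states: "Open label salbutamol and /or atrovent MDI will be provided as rescue medication". For methacholine effects, Section 2.3 names ipratropium: "Adverse effects are expected to be reversible with administration of an inhaled anticholinergic agent (ipratropium bromide) if necessary". For augmentation by BI 443651 it says: "Inhaled anticholinergic therapy should reverse these effects if required".

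**The concern.** The text and the table of one section give different answers for the same drug class, and the more permissive answer has no stated justification. The class matters here because the subjects have asthma, undergo repeated bronchoconstrictor challenges, and are supplied with a beta-agonist as one of two rescue drugs. Section 3.3.4.1, withdrawal criterion (a), expects that a subject whose FEV₁ falls by at least 45% may be symptomatic and need a short-acting beta-agonist. That a beta blocker opposes a beta-agonist is class pharmacology. The documents do not describe it or say how strong the opposition is.

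Three things are at stake: who may be enrolled, how well one of the rescue drugs would work in such a subject, and whether beta-blocker use counts as prohibited medication (category D1 in SAP Table 6.2:1).

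**Working it through.** The plan states no figure on this point, so the check compares texts and counts rows.

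**Step 1: table against text list.** Table 4.2.2.1:1 has 19 rows. Five allow some use:

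| Class in the table | Covered by the text list? |
|---|---|
| Inhaled corticosteroid, low dose, stable | Yes, by name |
| Paracetamol | Yes, by name |
| Short-acting beta-agonist, rescue only | Yes, through Section 4.2.1 |
| Short-acting anticholinergic, rescue only | Yes, through Section 4.2.1 |
| Beta blocker, stable | No |

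So 5 − 4 = 1 permitted class has no matching exception. The adverse-event relaxation cannot supply one, because the row concerns a drug already stable for 6 weeks before randomisation.

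**Step 2: the reverse direction.** The text allows medication for atopic conditions without limit. The table bars antihistamines, and systemic immunomodulators for allergic rhinitis or atopic dermatitis. The text is therefore looser than the table here. This is a separate mismatch.

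**Step 3: does another section settle it?**
- Exclusion 15 refers to Section 4.2.2 as a whole, which contains both versions.
- Exclusion 16 cites the table for permitted medications, but only as an exception to its long half-life rule.
- Exclusions 1 and 12 could keep a user out, but by judgement and without naming the class.
- Exclusion 11 names diuretics and renin-angiotensin drugs, not beta blockers.
- Section 3.3.2, to which the text points for washouts, gives only the 8-hour short-acting bronchodilator interval.

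None of these is a precedence rule. The table's specific, conditional row is nevertheless the natural one to follow, and exclusion 16 leans the same way.

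**Step 4: exposure of one enrolled user.** Challenges for a completing subject: 1 incremental at screening + 2 bolus × 4 periods = 9. Of the 8 bolus challenges, 3 follow active BI 443651. With 36 subjects, the planned minimum, one user is 1/36 = 2.8%. These figures describe exposure, not harm. The added risk cannot be computed from the documents.

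**Step 5: wording available for a fix.** Seven rows already bar a class from 4 weeks before screening and throughout the trial: oral and patch beta-adrenergics, antihistamines, cromolyn/nedocromil, mucolytics, antileukotrienes, theophylline, and electrolyte-altering drugs.

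**The case against.** The strongest reply is that a specific table row refines a general sentence. The table is headed as an overview of permitted and restricted medications, exclusion 16 treats it as a source of permitted drugs, and the beta-blocker row mirrors the inhaled-corticosteroid row. The atopic-medication mismatch shows that the text is loose summary prose. On that view the cure is to add beta blockers to the sentence. Much of this stands. A reader might infer that a site has no means of telling whether a user may be enrolled. That goes too far, since most sites would follow the row. But this reading is also the one under which the protocol permits beta blockers in challenged asthmatics without saying why, and adding words to the sentence would leave that unanswered.

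A second reply is that the safety argument is outside pharmacology and that the protocol already protects subjects. The textual mismatch does not need the pharmacology, and the protection is real. A reader might infer that a beta-blocker user would be left without effective rescue. The documents do not support that: ipratropium is the named reversal agent and Atrovent is a listed rescue option.

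A reader might also infer a biased treatment comparison. Nothing supports this either. The Part 2 primary analysis models change from each period's own baseline challenge with a random subject effect, and use held stable over all four periods would largely cancel within subject.

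**Conclusion.** The point holds as a minor eligibility and safety matter. One permitted class out of five has no basis in the text list, no reason is given, and no section says which version prevails. The likely operative reading is the permissive one. The number of users is unknown and may be zero, given that other significant conditions are excluded and other concomitant drugs are not foreseen.

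The mismatch rests on the documents alone. The safety part also assumes that a beta blocker opposes a beta-agonist to some degree, which the documents do not quantify. For the analysis, the only consequence shown is uncertainty over coding under category D1, which by default removes no subject from any analysis set.

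**What to change.** 1. Change the beta-blocker row of Table 4.2.2.1:1 to the prohibition used in the seven rows above (not allowed from 4 weeks before Visit 1 or during the trial). Add that a beta blocker must not be withdrawn in order to enter the trial, in line with the table's footnote 1 on bronchodilators and inhaled corticosteroid.
2. Add beta-blocker use in the 28 days before Visit 1 to exclusion 11.

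The cost is one table row and one sentence in a protocol amendment, and any beta-blocker user found at screening is not enrolled. Sample size, schedule and analysis do not change.

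This removes the beta-blocker mismatch only. A reader might infer that text and table would then agree throughout. They would not until the text's allowance for atopic medication is limited to what the table permits, which is a separate edit to the same sentence.

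If the sponsor wants to keep the permission, it should add beta blockers to the text list, give the reason, and reconcile this with exclusion 12. That cures the wording but keeps the class in the trial, so prohibition is preferable.

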4.2.2.2 Medication Restrictions (for Pulmonary Function Testing)

An 8-hour minimum washout period for inhaled short-acting bronchodilators (such as salbutamol and ipratropium) must be maintained. The morning dose of inhaled corticosteroids should not be taken in the 1-hour period prior to test-day (Day 1 and Day 2) pre-dose PFT.

Even if subjects violate these restrictions, as a general rule, scheduled procedures (including further dosing and methacholine challenge) should neither be postponed nor skipped. Regarding diet and lifestyle restrictions for forced spirometry testing please see Section 4.2.2.3.

